9.4.5. Baseline

Baseline is defined as the last assessment yielding non-missing valid values taken prior to the first dose of study drug. The same Baseline will be used for both Treatment Period and Extension Period.

9.4.6. Change From Baseline

Change from Baseline will be calculated as post-baseline value - Baseline value when both are not missing. If either value is missing, change from Baseline will be set to missing. The variable is for post-baseline visits only.

9.4.7. Body Mass Index

The BMI is derived as follows: $\text{weight (kg)} / [\text{height (cm)} / 100]^2$

9.4.8. Duration

Duration variables will be calculated in days as the end date – the start date + 1, unless otherwise specified.

Disease duration will be presented as the number of years between the date of the first infusion and the date of diagnosis.

9.4.9. Medications and Therapies

Concomitant medications/therapies are any medications/therapies with administration dates and times on or after the date and time of the first study drug dose. If the start date of a medication or therapy is partially or completely missing and the end (stop) date and time of the medication/therapy do not indicate that it occurred prior to the first dose, then the determination of concomitant status will be based on the following:

- If the start year is after the year of the first study drug dose, then the medication/therapy is concomitant; else,
- If the start year is the same as the year of the first study drug dose; and
 - The start month is missing, then the medication/therapy is concomitant; else if
 - The start month is present and is the same or after the month of the first study drug dose, then the medication/therapy is concomitant; else,
- If the start date is completely missing, then the medication/therapy is concomitant.

All other medications/therapies are considered prior medications/therapies and could occur from the 30 days prior to informed consent up to the Screening Period and prior to the first dose of study drug.

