- Standard of care medications for WD (trientine, penicillamine, and zinc) must be discontinued prior to the start of the Treatment Period (Day 1) with ALXN1840 and should not be used throughout the duration of study treatment.
- Vitamin E has been used as an adjunctive therapy in WD treatment regimens. Patients must not initiate use of vitamin E during the study.
- Patients must not use vitamins and/or minerals containing Cu, zinc, iron, or Mo.

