7.1.4. Prior and Concomitant Medications/Therapies

The World Health Organization (WHO) Drug Global version from Mar 2020 or later will be used to code the prior or concomitant medications/therapies. Medications will be summarized by Anatomic Therapeutic Chemical (ATC) Level 3 class and generic drug name.

Prior and concomitant medications will be summarized separately for the FA Set in the Treatment Period. The number and percentage of patients receiving any concomitant medication will be summarized, as well as the number and percentage of patients receiving any concomitant medication by ATC drug class and generic drug name. Patients reporting use of > 1 medication at each level of summarization (any medication received, ATC class, and generic drug name) will be counted only once. The ATC class terms will be displayed by descending order of incidence, as well as generic drug names within each ATC class. Prior medications used to treat WD and an additional analysis of all prior medications will be summarized similarly. Prior medications will be defined as medications that were discontinued prior to the start of study drug. Concomitant medications will be defined as medications that either started prior to the first dose of study drug and were continuing at the time of the first dose of study drug or started on or after the date of the first dose of study drug. If it cannot be determined whether a medication was stopped prior to the start of study drug dosing due to partial or missing medication start or end dates, it will be considered a concomitant medication. Further details on partial or missing dates can be found in [Appendix 9.4](#).

Prior and concomitant medications will be presented in a listing by patient and medication name.

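### The partial-date fallback in SAP 9.4.9 classes some continuing medications as prior, where SAP 7.1.4 classes them as concomitant

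*SAP*

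**What the plan says.** SAP 7.1.4 works from the stop date. "Prior medications will be defined as medications that were discontinued prior to the start of study drug". Concomitant medications include those that "started prior to the first dose of study drug and were continuing at the time of the first dose of study drug", as well as those begun on or after the first dose. Where it cannot be settled whether the medication had stopped, "due to partial or missing medication start or end dates, it will be considered a concomitant medication". The section then refers to Appendix 9.4 for further detail on partial or missing dates.

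SAP 9.4.9 opens with a compatible definition: "Concomitant medications/therapies are any medications/therapies with administration dates and times on or after the date and time of the first study drug dose". A separate rule follows for start dates that are partly or wholly missing. It applies when the end date and time "do not indicate that it occurred prior to the first dose, then the determination of concomitant status will be based on the following". Four start-date patterns then give concomitant status:

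- a start year after the first-dose year;
- the first-dose year with the month missing;
- the first-dose year with the same or a later month;
- a start date that is completely missing.

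For the remainder, "All other medications/therapies are considered prior medications/therapies".

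Protocol 6.5 says that trientine, penicillamine and zinc "must be discontinued prior to the start of the Treatment Period (Day 1) with ALXN1840" and bars them for the duration of study treatment.

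**The concern.** The 9.4.9 fallback is entered only when the end date has failed to show that the drug was finished before first dose. Under 7.1.4 every such medication is concomitant. Yet 9.4.9 then looks only at when the drug started and sends the earlier starts to prior. For a medication, an early start says nothing about whether it had stopped.

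The branching matches the adverse event rule in SAP 9.4.1. There the start date is the right test, because treatment emergence is defined by onset. It was probably carried over, though the SAP does not say so.

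What is at stake is the accuracy of two descriptive tables. Protocol 6.5 lets patients continue medications for existing conditions, so continuing drugs are expected. Protocol 5.1 requires at least a year of Wilson disease therapy before screening, and Protocol 6.5 records such drugs taken at any time before the study, so old start dates are certain and incomplete ones plausible. Any such record for a drug still in use would move from the concomitant table to the prior table. That includes a standard-of-care Wilson disease drug, if one were continued past Day 1.

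**Working it through.** The plan gives no figure to reproduce, so the check applies both rules as written to every feasible pattern of dates.

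**Inputs.** The 7.1.4 rule is prior if the end date shows the medication stopped before first dose, otherwise concomitant. The 9.4.9 rule is the four branches above plus the residual sentence. First dose is set to June 2020 for illustration only; the logic does not depend on the date.

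**Patterns.** There are 8 partial or missing start patterns and 4 end states (before first dose, on or after first dose, ongoing, missing), giving 8 × 4 = 32. Two are impossible, because a start after first dose cannot have an end before it. That leaves 32 − 2 = 30.

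An end date before first dose gives prior under both rules in all 6 feasible patterns. For the other three end states:

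| Start date (first dose June 2020) | 9.4.9 fallback | 7.1.4 | Agree? |
|---|---|---|---|
| Completely missing | concomitant | concomitant | yes |
| 2015, month missing | prior | concomitant | **no** |
| November 2019, day missing | prior | concomitant | **no** |
| 2020, month missing | concomitant | concomitant | yes |
| March 2020, day missing | prior | concomitant | **no** |
| June 2020, day missing | concomitant | concomitant | yes |
| August 2020, day missing | concomitant | concomitant | yes |
| 2021, month missing | concomitant | concomitant | yes |

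**Result.** Disagreements: 3 start patterns × 3 end states = 9 of 30. Agreements: 30 − 9 = 21. In all 9, the 9.4.9 fallback gives prior and 7.1.4 gives concomitant.

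**If the opening definition of 9.4.9 takes precedence.** Records with an end date on or after first dose (3) and ongoing records (3) become concomitant. The missing-end-date records (3) do not, because no administration after first dose is known. Remaining disagreements: 9 − 3 − 3 = 3.

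**Consistency check.** Under the 9.4.9 fallback, an ongoing drug with no start date at all is concomitant, while the same drug with start year 2015 is prior. Better information about the start yields the wrong class.

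**After the change proposed below.** Both rules use the end date in the same way, and the 9 disagreements become 0.

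These are counts of logical patterns. They do not estimate how many records in the trial are affected.

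**The case against.** The best defence is that the intended rule is clear. The opening sentence of 9.4.9 makes any drug with known administration after first dose concomitant. The residual sentence also describes its group as medications that could occur from 30 days before consent up to screening and before first dose, which does not fit a drug known to be in use later. SAP 7.1.4 supplies a definition and a default in the body of the plan: in doubtful cases "it will be considered a concomitant medication". It cites the appendix only for further detail.

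Part of this stands. The intention can be recovered, and on that reading 6 of the 9 disagreements go away. But 9.4.9 states that status for these partial starts is decided by the branches, so at best the section contradicts itself. The missing-end-date patterns still conflict with the 7.1.4 default, and a programmer who follows the reference to the appendix would code the wrong rule.

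A reader might also infer that the rule could hide prohibited Wilson disease therapy, or distort the Per Protocol Set. The documents do not support that:

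- The Schedule of Activities (Protocol Table 1) collects Wilson disease medication history at Screening and Day 1.
- Protocol 6.5 records medications throughout the study with start and end dates.
- SAP 7.1.4 lists every prior and concomitant medication by patient.
- SAP 7.1.2 has deviations determined and categorised before database lock.
- SAP 6.2.3 bases Per Protocol exclusions on important deviations agreed before lock. It does not use the concomitant medication table.

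**Conclusion.** The 9.4.9 fallback is wrong as written, and the severity is minor. For a partial start date in a year, or a month of the same year, before first dose, with an end date that is missing, ongoing or on or after first dose, it gives prior where 7.1.4 gives concomitant. The error runs one way: the concomitant summary is understated and the prior summary overstated.

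The consequence stops at those descriptive tables. The primary, sensitivity, secondary and exploratory analyses in SAP 7.2 contain no prior or concomitant term. For a Wilson disease drug to be misfiled, it would need both a partial early start date and use past Day 1 despite the prohibition. It would still appear in the by-patient listing and be open to deviation review.

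The number of records affected cannot be derived from the documents. It is tempting to express one patient as 1/24, about 4% of the evaluable patients. That is the share of any single patient and does not measure this defect; the medication tables also use the Full Analysis Set rather than the 24 evaluable patients. That long-running drugs often have incomplete start dates is an assumption. The finding itself rests only on the wording of the two sections.

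**What to change.** Replace the start-date branches in SAP 9.4.9 with an end-date rule that matches 7.1.4: a medication is prior only if its end date, complete or partial, shows that it stopped before the first dose of study drug. If the end date is on or after first dose, ongoing, missing or not decisive, the medication is concomitant. Keep the start-date logic in 9.4.1, where it belongs.

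The cost is a wording change in one SAP section and the matching derivation in the medication dataset. It needs no new data and alters no efficacy or safety analysis.

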9.4.10. MELD Score

The MELD score uses the patient's values for serum bilirubin, serum creatinine, and the INR to stratify severity of end-stage liver disease and was developed for transplant planning. The initial MELD score, $\text{MELD}_{(i)}$, is calculated according to the following formula:

$$\text{MELD}_{(i)} = 3.78 \times \ln[\text{serum bilirubin (mg/dL)}] + 11.2 \times \ln[\text{INR}] + 9.57 \times \ln[\text{serum creatinine (mg/dL)}] + 6.43$$

Creatinine, bilirubin, and INR values < 1.0 are set to 1.0, and creatinine values > 4.0 are set to 4.0 when calculating $\text{MELD}_{(i)}$. Additionally, creatinine, bilirubin, and INR are rounded to the tenth decimal place prior to performing the calculation. The initial MELD score is then rounded to the nearest integer. The maximum MELD score is 40.

A modification to the MELD score exists for MELD scores > 11 ([Alcorn, 2015](#)) and this will be applied to remain up to date with the current guidance. Thus, if $\text{MELD}_{(i)}$ is > 11, the MELD score is recalculated as follows:

$$\text{MELD} = \text{MELD}_{(i)} + 1.32 \times (137 - \text{sodium (mmol/L)}) - 0.033 \times \text{MELD}_{(i)} \times (137 - \text{sodium (mmol/L)})$$

Sodium values < 125 mmol/L will be set to 125, and values > 137 mmol/L will be set to 137.

The MELD score will be calculated each time the appropriate clinical chemistry parameters are obtained at visits listed in Section 9.1. If any of the parameters required to compute the MELD score are unavailable at any given visit, the MELD score will not be derived for that patient visit.

9.4.11. Modified Nazer Score

The modified Nazer score will be calculated by a central laboratory at visits listed in Section 9.1. If any of the 5 parameters required to compute the modified Nazer score are unavailable at any given visit, the modified Nazer score will be set to missing for that patient visit.

The score for an individual analyte (bilirubin, AST, INR, leukocytes, and albumin) should be derived from Table 3, and then, all 5 scores will be added to get the final score.

Table 3: Modified Nazer Score

Score	Bilirubin ($\mu\text{mol/L}$)	AST (IU/L)	INR	Leukocytes ($10^9/\text{L}$)	Albumin (g/L)
0	0-100	0-100	0-1.29	0-6.7	>45
1	101-150	101-150	1.3-1.6	6.8-8.3	34-44
2	151-200	151-300	1.7-1.9	8.4-10.3	25-33
3	201-300	301-400	2.0-2.4	10.4-15.3	21-24
4	> 301	> 401	> 2.5	> 15.4	< 20

Abbreviation: AST = aspartate transaminase; INR = international normalized ratio.

9.4.12. CLDQ

The CLDQ is a 29-item instrument with 6 domains (Fatigue, Activity, Emotional function, Abdominal symptoms, Systemic symptoms, Worry) that measures longitudinal change over time in patients with chronic liver disease. Each domain is scored from 1 (worst possible function) to 7 (best possible function). Scoring of the questionnaire is performed by dividing each domain score by the number of items per domain. Overall CLDQ score is obtained by adding scores for each item and dividing by the total number of items.

9.4.13. TSQM-9

The TSQM has 9 questions making up 3 components: effectiveness score, convenience score, and global satisfaction score. Details on deriving the component scores are given below, including how to handle a single missing question within a component. If > 1 question is missing for a component, the component score cannot be derived.

The effectiveness score is composed of Questions 1 to 3, each of them ranging from 1 to 7. The score is calculated as follows: $(Q1+Q2+Q3-3)/18 \times 100$. If one of the questions is missing, the score is calculated as follows (including the missing item): $(Q1+Q2+Q3-2)/12 \times 100$.

The convenience score is composed of Questions 4 to 6, each ranging from 1 to 7. The score is calculated as follows: $(Q4+Q5+Q6-3)/18 \times 100$. If one of the questions is missing, the score is calculated as follows (including the missing item): $(Q4+Q5+Q6-2)/12 \times 100$.

The global satisfaction score is composed of Questions 7 to 9, where Questions 7 and 8 range from 1 to 5 and Question 9 ranges from 1 to 7. The score is calculated as follows: $(Q7+Q8+Q9-3)/14 \times 100$. If either Question 7 or 8 is missing, the score is calculated as follows (including the missing item): $(Q7+Q8+Q9-2)/10 \times 100$. If Question 9 is missing, the score is calculated as follows: $(Q7+Q8-2)/8 \times 100$.

9.4.14. UWDRS

The algorithms for calculating the UWDRS subscores and subscales are given below. The UWDRS total score will be the sum of the 3 subscores.

UWDRS I: Consciousness; Maximum score of 3

- Set to Question 1, range 0 to 3.

UWDRS II: Disability; Maximum score of 40

- Calculate the sum of Question 2 to Question 11, each question has range 0 to 4
- If all 10 items are populated, the subscore will be the sum calculated above. If 8 or 9 items are populated, pro-rate the score by dividing by the number of answered items and multiplying by 10. This is done in order to estimate the value the patient could have achieved if they had answered all the questions. If < 8 items are populated, the score will not be derived.
 - For example, a patient has answered 8 of 10 questions and the total of his or her answered questions is 23. The pro-rated score will then be calculated as follows: $23/8 \times 10 = 28.75$.

UWDRS III: Neurological Status; Maximum score of 175

- Calculate the following new scores for Questions 12 to 34:
 - Question 12: range 0 to 4
Set to Q12A
 - Question 13: range 0 to 6
If Q13=0 then set to 0;
else if Q13=1 then do;
if Q13A>2 then set to Q13A
else set to Q13A+Q13B
end;
 - Question 14: range 0 to 1
Set to Question 14
 - Question 15: range 0 to 16
Set to Q15A+Q15B+Q15C+Q15D
 - Question 16: range 0 to 4
Set to Q16

- Question 17: range 0 to 20
Set to Q17A+Q17B+Q17C+Q17D+Q17E
- Question 18: range 0 to 8
Set to Q18A+Q18B
- Question 19: range 0 to 8
Set to Q19A+Q19B
- Question 20: range 0 to 4
Set to Q20
- Question 21: range 0 to 16
Set to Q21A1+Q21A2+Q21B1+Q21B2
- Question 22: range 0 to 8
Set to Q22A+Q22B
- Question 23: range 0 to 8
Set to Q23A+Q23B
- Question 24: range 0 to 8
Set to Q24A+Q24B
- Question 25: range 0 to 4
Set to Q25
- Question 26: range 0 to 8
Set to Q26A+Q26B
- Question 27: range 0 to 4
Set to Q27
- Question 28: range 0 to 10
If Q28=0 then set to 0;
else if Q28=1 then do;
 if Q28A>2 then set to Q28A
 else set to Q28A+Q28B+Q28C
end;
- Question 29: range 0 to 10
If Q29=0 then set to 0;
else if Q29=1 then do;
 if Q29A1+Q29A2>2 then set to Q29A1+Q29A2
 else set to Q29A1+Q29A2+Q29B+Q29C
end;

- Question 30: range 0 to 24
Set to Q30A+Q30B+Q30C+Q30D+Q30E+Q30F
- Question 31: range 0 to 1
Set to Q31
- Question 32: range 0 to 1
Set to Q32
- Question 33: range 0 to 1
Set to Q33
- Question 34: range 0 to 1
Set to Q34
- Add up the newly calculated scores for Questions 12 to 34. If all 23 items are completely populated, the subscore will be that sum. If 20 to 22 items are fully populated, then calculate the maximum score of the answered items. Next, divide the sum of the responses to Questions 12 to 34 by the maximum score and multiply by 175 to obtain the subscore. This is done in order to estimate the value the patient could have achieved if they had answered all the questions. If < 20 items are fully populated, then do not derive. If part of a multi-component question is answered, the maximum score of the answered components will be used to derive the subscore. However, partially answered questions will not be considered as fully populated (and therefore, will be viewed as a null response) when counting the number of fully answered questions in order to obtain a minimum of 20 fully answered questions. The exception to this latter rule is for Questions 13, 28, and 29. If the > 2 condition is met with populated components, the question is considered to be fully populated regardless if the unused components are null.
 - For example, a patient has responded to 21 questions and left Questions 21 and 22 null. The total of their responses to the answered questions is 97 and the maximum score of the answered questions is 151. The pro-rated score will then be calculated as: $97/151 \times 175 = 112.41721854$.
 - For example, a patient has responded to 22 questions and part of Question 17 so they will be considered as answering 22 questions. The total of their response to the answered questions is 111 and the maximum score of the answered questions and answered components (including any partially answered questions) is 167. The pro-rated score will then be calculated as $111/167 \times 175 = 116.317365$.

UWDRS II Activities of Daily Living (ADL): Mobility, Feeding, Dressing, Grooming, Taking a Bath or Shower, and Toilet Use; Maximum score of 10

- Take average of the transformed items for Q2, Q7, to Q11

UWDRS II Individual symptoms:

- Salivation: Q5, range 0 to 4
- Swallowing: Q6, range 0 to 4

UWDRS III Tremor: Tremor at Rest, Head Tremor, Tremor in Arms, Postural Tremor Lower Extremity, and Finger-to-Nose Test; Maximum score of 10

- Take average of the transformed items for Q15, Q16, Q21, Q22, Q24

UWDRS III Dystonia: Speech, Facial Expression, Rigidity, Finger Taps, Rapid Alternating Hand Movements, Handwriting, Leg Agility, Cervical Dystonia, Arm and Hand Dystonia, Arising from Chair, Posture, and Gait; Maximum score of 10

- Take average of the transformed items for Q12, Q13, Q17 to Q20, Q23, and Q25 to Q29.

UWDRS III Individual symptoms

- Speech: Q12, range 0 to 4.
- Handwriting: Q20, range 0 to 4.

For each new subscale (ADL, Tremor, Dystonia), at least 50% of items need to be answered in order to calculate new subscale. In order to standardize responses, these items will be transformed to a 0 to 10 scale and then take the average of the transformed items.

- For single-item score, divide the score by the range of options (0-4, then divide by 4) to transform it to 0-1 and then multiplied by 10.
- For multi-item score, prorate on the number of sub-items been answered (Q15, Q17, Q18, Q19, Q21, Q22, Q23, Q24, and Q26).
 - For example, Question 15 is a multi-component item – Tremor at rest. There are 4 components: 1) Left Upper Extremity; 2) Right Upper Extremity; 3) Left Lower Extremity; and 4) Right Lower Extremity. These 4 components were summed to create “Item 15”, which had a possible range of “0-16” If < 4 sub-component scores were available, use the possible range for the number of items that were answered (e.g., if 3 components were available, then the range was 12).
 - For item 13 (maximum score =6), item 28 (maximum score=10) and item 29 (maximum10), use fixed maximum score to standardize the score.

For the individual symptom scale (salivation, swallowing, speech, and handwriting), the original scale (0-4) will be used.

9.5. Additional Details on Statistical Methods

The reference SAS codes used for efficacy analyses are as follows:

Multiple Imputation

Step 1:

```
proc mi data=xxx nimpute=20 seed=54321 out=yyy;  
  mcmc impute=monotone;  
  var BASE W48;  
run;
```

Step 2:

```
proc ttest data=xxx;  
  by _imputation_;  
  paired BASE*W48;  
run;
```

Step 3:

```
proc mianalyze data=xxx;  
  by AVISIT;  
  modeleffects ESTIMATE;  
  stderr STDERR;  
run;
```

Paired sample t-test

```
proc ttest data=xxx;  
  paired BASE*W48;  
run;
```

Wilcoxon Signed-rank test

```
proc univariate data=xxx;  
  var CHG;  
run;
```

MMRM

```
proc mixed data=xxx method=reml;  
  class AVISITN USUBJID;  
  model CHG=AVISITN BASE / solution ddfm=kr cl;  
  repeated AVISITN / subject=USUBJID type=UN;  
  lsmeans AVISITN / cl;  
run;
```

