9.4.1. Efficacy Analyses

9.4.1.1. Treatment Period

The primary objective of this study is to evaluate change in liver Cu concentration following treatment with ALXN1840 at 48 weeks in patients with WD. The primary analysis will be performed using the Full Analysis Set in the Treatment Period.

The change in liver Cu concentration will be evaluated using a paired samples t-test. For the primary analysis, a multiple imputation method will be used for missing data imputation.

Missing values for each patient will be imputed multiple times based on the estimated means from patients with similar baseline liver Cu concentration values. This approach will be used for all missing data at Week 48 due to any reason including, but not limited to, loss to follow-up and withdrawal of consent. The details of implementing this multiple imputation approach are as follows:

- Step 1: Missing values at Week 48 will be imputed 20 times via SAS PROC MI, using MCMC statement, including baseline and Week 48 liver Cu value; imputed values at Week 48 will be retained in the imputed datasets.
- Step 2: Apply paired samples t-test analysis for each of the 20 imputed datasets and save the mean and standard error at Week 48 from each of the 20 analyses.
- Step 3: Combine the 20 sets of analysis results via SAS PROC MIANALYZE. The combined treatment effect, confidence interval, and p-value will be estimated.

Sensitivity analyses will be performed to assess the robustness of the analysis result and will include:

- Use baseline value carried forward to impute missing Week 48 data
- Analyze primary endpoint using the Per Protocol Set, multiple imputation will be used to impute missing Week 48 data

Secondary and exploratory analyses will be performed using the Full Analysis Set in the Treatment Period.

For continuous endpoints that are measured multiple times between baseline and Week 48, data will be analyzed using mixed model repeated measures (MMRM) analysis. Fixed-effect terms will include visit and baseline value as covariates. An unstructured covariance will be used to model within-patient error.

For exploratory endpoints, data will be analyzed as observed, for endpoints that are only measured at baseline and Week 48, an analysis of covariance (ANCOVA) model will be used to analyze continuous endpoints, and a non-parametric ANCOVA model will be used to analyze ordinal outcomes. Baseline value will be included in the model.

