6.2.2. Full Analysis (FA) Set in the Treatment Period

The Full Analysis (FA) Set in the Treatment Period is defined as all patients who receive at least 1 dose of study drug in the Treatment Period and have at least a Baseline liver Cu value evaluable. This population will be used for the primary, secondary, and exploratory efficacy analyses.

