7.2.1. Primary Analysis

The primary objective of this study is to evaluate change from Baseline in liver Cu concentration following treatment with ALXN1840 at Week 48 in patients with WD. The primary analysis will be performed using the FA Set in the Treatment Period.

To assess the reduction in liver Cu concentration, liver biopsies will be taken during the Screening Period and at Week 48 of Treatment Period, where the assessment from Screening will be regarded as Baseline. The change from Baseline in liver Cu concentration will be evaluated using a paired sample t-test on Baseline and Week 48 assessment values.

Prior to the primary analysis, multiple imputation will be used to impute missing data at Week 48 due to any reason based on Baseline values. Missing values at Week 48 will be imputed 20 times via SAS PROC MI, using the MCMC method, including Baseline and Week 48 liver Cu assessment values. A paired sample t-test analysis will be applied for each of the 20 imputed datasets, and then 20 sets of analysis results will be combined afterward via SAS PROC MIANALYZE. The combined estimate of the treatment effect, standard error (SE), 95% CI, and p-value will be summarized.

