7.2.1.1. Handling of Dropouts or Missing Data

For missing liver Cu concentration data at Week 48, the multiple imputation method will be used for the primary analysis and sensitivity analysis. Details for multiple imputation can be referred to in Section 7.2.1, and an example of SAS code can be referred to in Section 9.5. The Baseline value carried forward method will also be used in the second sensitivity analyses, where missing Week 48 values will be imputed to Baseline values.

Note: Liver Cu concentrations reported as < LLOQ or > ULOQ will be considered non-evaluable. Non-evaluable data will be excluded when deriving summary statistics in both liver Cu primary analysis and Cu sensitivity analysis. This same principle will also be applied to the analysis of other live metals.

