7.2.1.5. Sensitivity Analyses

Three sensitivity analyses will be performed to assess the robustness of the analysis result, as follows:

- Similar to the primary analysis but use Baseline value carried forward to impute missing Week 48 data instead
- Similar to the primary analysis but use the observed data from patients where both Baseline and Week 48 data are available instead
- Similar to the primary analysis but use the PP Set in the Treatment Period instead

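### The reference code for the primary analysis imputes no Week 48 liver copper values, so it contradicts the text and reproduces the observed-pairs sensitivity analysis

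*SAP*

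**What the plan says.** The text of both documents agrees. SAP 7.2.1 states: "Missing values at Week 48 will be imputed 20 times via SAS PROC MI, using the MCMC method". Protocol 9.4.1.1, Step 1, adds that "imputed values at Week 48 will be retained in the imputed datasets". Each completed data set then goes to a paired t-test, and the 20 results are pooled with PROC MIANALYZE.

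For the implementation, SAP 7.2.1.1 says that "an example of SAS code can be referred to in Section 9.5". In that section, Step 1 calls PROC MI with "mcmc impute=monotone" and a variable list of BASE followed by W48. Step 2 runs PROC TTEST with "paired BASE*W48". Step 3 begins "proc mianalyze data=xxx" and passes only the estimate and its standard error. No further imputation step appears between Steps 1 and 2.

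Two other places matter. SAP 6.2.2 admits patients to the Full Analysis (FA) Set only if they "have at least a Baseline liver Cu value evaluable". SAP 7.2.1.5 lists, as a separate sensitivity analysis, one that will "use the observed data from patients where both Baseline and Week 48 data are available instead".

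**The concern.** In PROC MI, `impute=monotone` does not complete the data. It fills only the cells needed to turn an arbitrary missing pattern into a monotone one, and a second imputation step normally follows. Here the pattern is monotone from the start, so the statement has nothing to do. The 20 output data sets are copies of the input, and PROC TTEST drops every incomplete pair.

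Text and code therefore define two different primary estimates. If the code is followed, agreement between the primary analysis and the observed-pairs sensitivity analysis is guaranteed and says nothing about robustness to dropout. Any association between dropout and baseline copper goes uncorrected in the primary result. The Per Protocol analysis does not help, because SAP 6.2.3 requires both values and so leaves nothing to impute. Baseline carried forward would be the only one of the four analyses that handles missing Week 48 data.

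Two smaller points sit in the same code block. Step 3 does not give PROC MIANALYZE the complete-data degrees of freedom (the EDF option), so pooling uses the large-sample formula in a study of 24 to 28 patients. Step 2 computes baseline minus Week 48, opposite in sign to SAP 9.4.6 and to the alternative hypothesis; the two-sided p-value is unaffected.

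**Working it through.** **The plan's own figure.** Protocol 9.2 and SAP 9.3 give 24 evaluable patients, reduction 228, SD of paired difference 319 and one-sided level 0.025. The noncentrality is 228 / (319/√24) = 3.50 on 23 df, giving power 91.8%. The stated 92% reproduces. With 28 enrolled and 15% dropout, 28 × 0.85 = 23.8, so about 4 patients lack a Week 48 value.

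**What Step 1 fills.** Under the monotone rule a missing cell is filled only if a later variable in the list is observed. BASE is never missing in the FA Set, and W48 is last in the list, so no W48 cell qualifies. The rule was applied directly, without running SAS, to simulated trials of 28 patients with 4 missing:

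- 0 of 4 values were filled and between-imputation variance was 0.
- The pooled mean matched the complete-case mean to about 1e-13, and the pooled standard error was the complete-case one.
- Full imputation filled all 4, with between-imputation variance averaging about 360 to 740.

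**Size of the difference.** The documents give neither the baseline SD nor the baseline to Week 48 correlation ρ. Assume equal variances and ρ from 0.3 to 0.7. Then baseline SD = 319/√(2(1−ρ)), and the regression slope of change on baseline is −(1−ρ). If the 4 dropouts lie d SDs above the FA Set baseline mean, the 24 completers lie (4/24)d SDs below it. The observed-pairs reduction is then smaller than the imputed one by

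shift = 319 × √((1−ρ)/2) × (4/24) × d

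| ρ | d = 1 | % of 228 | d = 0.5 |
|---|---|---|---|
| 0.3 | 31.5 µg/g | 13.8% | 15.7 µg/g |
| 0.5 | 26.6 µg/g | 11.7% | 13.3 µg/g |
| 0.7 | 20.6 µg/g | 9.0% | 10.3 µg/g |

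Replacing 4/24 by 2/26 (2 missing) gives 9.5 to 14.5 µg/g at d = 1; 6/22 (6 missing) gives 33.7 to 51.5. The formula is symmetric: with d = −1 the observed pairs overstate the reduction by the same amount.

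**Simulation** (40,000 replicates per cell, 20 imputations, normal regression of Week 48 on baseline, Rubin pooling, 4 missing, true change −228). With dropout odds rising with baseline, so that dropouts averaged 0.81 SD above the mean, observed pairs gave −202.3, −206.9 and −211.1 at ρ = 0.3, 0.5 and 0.7. Imputation gave −227.9, −228.4 and −227.8. With dropout unrelated to baseline neither was biased, but the two estimates should still differ by 9 to 12 µg/g on average. As coded they differ by 0.

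**Step 3, once imputation is repaired.** Two-sided type I error at nominal 5%:

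| Missing | Without EDF | EDF = 27 |
|---|---|---|
| 2 | 5.8–6.0% | 4.6–4.8% |
| 4 | 5.5–5.7% | 4.4–4.5% |
| 6 | 5.6–5.8% | 4.3–4.4% |

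With 4 missing, the median pooled df is about 1,000 to 1,570 without EDF and 21 to 22 with it.

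**Step 3 as coded.** Between-imputation variance is 0, so Rubin's df has no finite value. If the software treats it as infinite, 1.96 replaces the 23-df critical value of 2.069. The two-sided error is then 6.2%, and the interval half-width is 1.96 × 319/√24 = 127.6 instead of 134.7 µg/g. How the software reports this case was not tested; it may return no usable p-value.

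**The case against.** The strongest reply is that the code does not govern. SAP 7.2 calls it sample code and SAP 7.2.1.1 an example, while the text is clear and consistent across both documents. The block is also schematic: Step 1 writes one data set and Step 2 reads another placeholder name, nothing saves the t-test estimate and standard error, and Step 3 is run by a visit variable that the two-column layout does not contain. A programmer must adapt it. That is true, but all of those gaps can be repaired while the imputation option is copied unchanged, and the result would still be a plausible estimate and standard error. Nothing elsewhere in the SAP names or corrects the option.

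The second reply is that the practical effect is limited. With dropout unrelated to baseline, a separate simulation found that the imputed and observed-pairs tests disagreed on significance in about 3% of trials at the planned effect and about 2% under the null. Observed pairs kept the planned power (91.6 to 92.4%), since the sample size was set for 24 evaluable patients. Where high-copper patients drop out, the uncorrected estimate works against the drug, with power about 86 to 87%. Nothing in the documents says dropout will depend on baseline copper. All of this stands. It bears on how much the result might move, not on whether the primary analysis is specified consistently.

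It is also fair that baseline carried forward does not use this code path, that omitting EDF contradicts no statement in the protocol, and that the sign of the difference is presentational.

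**Conclusion.** The concern holds. For the FA Set as defined, the Step 1 code imputes nothing, and following it makes the primary estimate identical to the observed-pairs sensitivity estimate. The contradiction concerns the primary endpoint and should be removed whatever its numerical size; this conclusion rests on Step 1 alone.

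The magnitudes are illustrative. They rest on 28 patients with 4 missing, SD of change 319, and assumed equal variances and correlation. Under a different assumption (Week 48 SD 0.8 times a baseline SD of 300 to 500) and a more extreme pattern, with the 4 highest-baseline patients missing, the average shift was about 48 to 56 µg/g. The missing EDF is a modest, secondary source of liberality. The meaning of the imputation option is standard software behaviour; the sponsor can confirm it by counting missing W48 values in the PROC MI output.

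**What to change.** - **SAP 9.5, Step 1:** change the statement to `mcmc impute=full;`. This keeps the MCMC method named in both documents. Confirm that no W48 value is missing in the output data set.
- **Secondary, Step 3:** add EDF equal to the FA Set size minus 1 to PROC MIANALYZE, and say so in SAP 7.2.1.
- **Presentational, Step 2 and the stand-alone t-test:** use `paired W48*BASE`, so that a reduction is negative as in SAP 9.4.6.
- Check any program already written or run against the corrected code.

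The cost is four code statements and one sentence. Sample size and planned power do not change. With EDF the confidence interval is about 6% wider than pooling without it (critical value about 2.07 at 22 df against 1.96). Programs already run may need rerunning.
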